Statistical analysis	
Data processing and statistical analysis will be carried out by the service provider, Axonal-Biostatem.
 
The statistical analyses will be described in a Statistical Analysis Plan (SAP) validated by the Sponsor and the Scientific Committee, prior to the freeze-in.
 
Statistical analyses will be performed after baseline freezing of the data with SAS® software (SAS Institute, NC, Cary, USA), version 9.4 or later.
 
Demographic and efficacy/performance analyses will be performed in the ITT population. The primary endpoint will be analyzed in PP (Per Protocol) and then validated in the ITT (intention to treat) population. The safety analyses will be performed in the safety population.
 
For quantitative variables, the usual statistics (n, missing n, mean, standard deviation (SD), median, first and third quartiles (Q1 and Q3), minimum and maximum) will be presented. IC95% may be

	
presented if relevant (especially for the primary endpoint).
 
For categorical variables, the usual statistics (n, missing n, frequency and percentage) for each modality will be provided.
 
Descriptive statistics will be provided in aggregate and by pump group.
 
The type 1 error, α, is set at 5% when the tests used will be two-sided (superiority) and α will be set at 2.5% when the tests will be one-sided in the case of Noninferiority (IC95%).
 
Analysis of the main objective
 
The non-inferiority analysis will be produced via an Ancova or mixed model on the Per-Protocol population and then on an intention-to-treat basis.
 
If non-inferiority is demonstrated, a superiority analysis will be conducted.
 
Analysis of secondary objectives
 
The secondary criteria will be described and then be the subject of mixed or Ancova models.
 
A non-inferiority analysis on HbA1c data and superiority analyses on Time in range, number of glycemic events, patient satisfaction will be performed.

Regulatory framework	ID-RCB number, CPP opinion, CNIL MR001 and RGPD compliance, information to the ANSM, approval of investigator contracts by the CNOM, transparency obligations
Logistics	CRO Axonal-Biostatem (Nanterre, France)

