6.3 PROHIBITED TREATMENTS

Investigators are free to manage their patients with diabetes as usual, but any treatment should be documented during the study, as well as any changes in treatment during the study. Therefore, there are no prohibited treatments during the study.

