4.4.3 Calculated/derived criteria

			2 = "More than 10 years
Number of years and months of treatment per pump	PUMP_D = Number of years * 12 + number of months	Time since starting pump therapy (in months)	Digital
Weight (kg) and height (cm)	BMI_D = (weight/height ²)*10000	Body Mass Index (BMI)	Digital
IMC_D	IMC4CL_D = -0 if BMI_D<18.5 -1 if BMI_D = [18,5 ; 25[-2 if BMI_D = [25; 30[. -3 if BMI_D >= 30	BMI (in classes)	0 = "Less than 18.5 1 = " [18,5 ; 25[" 2 = " [25 ; 30[" 3 = "Greater than 30
Tolerance variables	AL_PBTOL_D = -1 if the patient reported during the follow-up an irritation/itching problem or a redness problem or another adverse event -0 otherwise	Patient with at least one tolerance problem	0 = "No 1 = "Yes
HbA1c value measured in the laboratory at D0 and 3M	EVOL_HBA1C_D = HbA1c at M3 - HbA1c at D0	Evolution of HbA1c between D0 and 3M	Digital
Estimated HbA1c (FSL) (%)	EVOL_eHbA1c = HbA1c estimate at V2 - HbA1c estimate at D0 (will also be calculated for V3 and V4)	Evolution of HbA1c estimation between D0 and V2,V3,V4	Digital
Average blood glucose at different follow-up times	EVOL_GLYC_V2 = Average blood glucose at V2 - Average blood glucose at D0 (will also be calculated for V3 and V4)	Evolution of the average blood glucose level between D0 and V2, V3, V4	Digital
Average daily basal dose at different follow-up times	EVOL_BASAL_V2 = Average daily basal dose at V2 - Average daily basal dose at D0 (will also be calculated for V3 and V4)	Evolution of the average daily basal dose between D0 and V2, V3, V4	Digital
Average daily bolus dose at different follow-up times	EVOL_BOLUS_V2 = Average daily bolus dose at V2 - Average daily bolus dose at D0 (will also be calculated for V3 and V4)	Evolution of the average daily bolus dose between D0 and V2, V3, V4	Digital

Number of Boluses/day at different follow-up times	EVOL_NB_BOLUS_V2 = Number of Boluses/day at V2 - Number of Boluses/day at D0 (will also be calculated for V3 and V4)	Evolution of the number of Bolus/day between D0 and V2, V3,V4	Digital
Time of wearing the FSL	PORT_70sup = -1 wear time greater than 70%. -0 otherwise	FSL wear time greater than 70%.	0 = "No 1 = "Yes

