7.3 PATIENT CHARACTERISTICS AT INCLUSION

Inclusion parameters will be described globally and according to their group allocated by randomization on the **ITT population and then on the ITTm population**. Only demographic data will be described for **patients discharged with COVID-19**. Demographics

- Age (years)
- Gender (female; male)
- Type of diabetes (type 1; type 2)
- Time since the discovery of diabetes
- Time since discovery of diabetes (<5 years; 5-10 years; >10 years)

- Type of diabetes treatment:
 - Time since starting pump therapy (months)

Associated oral treatment

- For patients with type 2 diabetes:
 - Associated oral treatment (yes; no)
 - The list of associated oral treatments will be given via a listing

Clinical examination

- Weight (kg)
- Size (cm)
- BMI calculated (kg/m²)
- BMI calculated in classes (Lean: <18.5 kg/m²; Normal: 18.5-<25 kg/m²; Overweight: 25-<30 kg/m²; Obese: >= 30 kg/m²)
- Heart rate (bpm)
- Systolic blood pressure (mmHg)
- Diastolic blood pressure (mmHg)

Biological data

• Last HbA1c measurement in the laboratory (%)

Sensor data

- Estimated HbA1c (FSL) (%)
- FSL Wear Time (%)
- FSL wear time > 70% (yes; no)
- Average blood glucose (FSL) (mg/dl)
- Blood glucose SD (FSL) (mg/dl)
- Coefficient of variation of glucose values (%)
- Number of hypoglycemia
- Time spent in hypoglycemia <70 mg/dl (%)
- of normoglycemic values > 70-180 mg/dl (%)
- Time spent above >180 mg/dl (%)

Pump data

- Name of insulin used (Novorapid; Humalog; Apidra; Other)
 - If other, details will be given in a listing
- Average total daily insulin dose:
 - Average Daily Basal Dose
 - Average daily bolus dose
 - Number of Boluses/day

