- Responses to the Medtrum A7+ and Omnipod pump satisfaction questionnaires. Comparisons between pump groups of responses will be made using Student's t test or Mann and Whitney test if relevant or applicable.
- Answers to the specific questionnaire related to preference

7. Insulin treatment

The following criteria will be described for each period and per pump group, comparisons between groups will be made using Student's or Mann and Whitney test:

- Total dose administered daily (sum Basal + Bolus)
- Average Daily Basal Dose
- Average daily bolus dose
- Number of Boluses/day

The evolution of these criteria in relation to the baseline will be described at each stage.

Additional insulin injections with a pen during the study will be listed.

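### Insulin dose is compared between pumps only as an unadjusted level in each period; adjusting for D0 dose would give a more precise comparison at little cost

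*SAP*

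**What the plan says.** SAP 7.4.2 item 7 lists total daily dose, basal dose, bolus dose and boluses per day. These are described "for each period and per pump group, comparisons between groups will be made using" Student or Mann-Whitney tests, with no covariate. The next statement on these variables is "The evolution of these criteria in relation to the baseline will be described at each stage". No between-group test, adjusted estimate or confidence interval is named for the change.

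Baseline dose does appear elsewhere in the SAP. Section 7.3 describes "Average total daily insulin dose" by group at inclusion, with its basal and bolus parts and boluses per day. Section 4.4.3 derives changes from D0, for example "EVOL_BASAL_V2 = Average daily basal dose at V2 - Average daily basal dose at D0" and "EVOL_BOLUS_V2 = Average daily bolus dose at V2 - Average daily bolus dose at D0", and does the same for boluses per day, at V2, V3 and V4. It derives no such variable for total daily dose.

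The protocol gives two methods for secondary endpoints. The synopsis says: "The secondary criteria will be described and then be the subject of mixed or Ancova models". Section 11.2.4 of the protocol body gives t or Mann-Whitney tests for quantitative variables and lists insulin doses among the endpoints covered. SAP section 6 records no change to the protocol's analyses.

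**The concern.** The trial is open-label. Protocol 3.2 has patients determine their own doses, and under 6.3 "Investigators are free to manage their patients with diabetes as usual". Equal sensor-estimated HbA1c is therefore compatible with unequal insulin use. Delivered dose is the most direct evidence on that, and a reader of a non-inferior result will want to see it.

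Every patient enters on Omnipod, so the D0 dose is that patient's own reference on the comparator pump. A test on follow-up levels alone leaves this reference out. The SAP does not treat its other main outcomes this way: the primary endpoint is adjusted for its baseline value, and laboratory HbA1c (7.4.2 item 1) is compared as a change. What is at stake is how sensitive and how readable the between-pump dose comparison is.

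**Working it through.** **The plan's own figures.** The documents give no SD, sample size or power for insulin dose. The stated sample sizes concern the primary endpoint and reproduce: 2 × (1.96 + 0.842)² × 0.55² / 0.4² = 29.7, so 30 per group; with SD 0.8 it is 62.8, so 63 per group; and 60 / 0.8 = 75.

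**Inputs.**
- Analysis set: ITTm, at most 100 − 4 = 96 patients (SAP 5.1 and 7.1.3), so about 48 per arm under 1:1 allocation with no missing dose.
- Two-sided alpha 5% (protocol synopsis).
- Assumed: dose SD 12 IU/day (range 8 to 15), and baseline to follow-up correlation r from 0.5 to 0.9.

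**Precision.** The unadjusted SE is SD × √(2/48) = 12 × 0.204 = 2.45 IU/day. The 95% half-width is 1.986 × 2.45 = 4.9 IU/day. ANCOVA on the D0 dose multiplies this by √(1 − r²). The difference detectable with 80% power is (1.96 + 0.842) × 0.204 = 0.57 SD unadjusted, with the same multiplier for ANCOVA. The last column is the power for a true difference of 0.33 SD, which is 4 IU/day at SD 12.

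| Analysis | Multiplier | Half-width (IU/day) | Detectable (SD) | Power at 0.33 SD |
|---|---|---|---|---|
| Unadjusted level | 1 | 4.9 | 0.57 | 37% |
| ANCOVA, r = 0.5 | 0.866 | 4.2 | 0.50 | 46% |
| ANCOVA, r = 0.7 | 0.714 | 3.5 | 0.41 | 62% |
| ANCOVA, r = 0.8 | 0.600 | 2.9 | 0.34 | 77% |
| ANCOVA, r = 0.9 | 0.436 | 2.1 | 0.25 | 96% |

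At SD 12, the detectable difference is 0.57 × 12, about 6.9 IU/day, unadjusted and 0.34 × 12, about 4.1 IU/day, with ANCOVA at r = 0.8. Over SD 8 to 15, the unadjusted half-width runs from 3.2 to 6.1 IU/day, and the ANCOVA half-width at r = 0.8 from 1.9 to 3.6.

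Testing the change score instead has multiplier √(2(1 − r)). That beats the unadjusted level only when r exceeds 0.5. ANCOVA is at least as precise as either at any r.

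**Validity.** In 20,000 simulated trials with 48 per arm and r = 0.8, the unadjusted t test had a type I error of 4.8% against a nominal 5%.

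**Effect of a baseline imbalance in one trial.** Given a baseline gap g, the expected unadjusted difference is the true effect plus r × g, with SD equal to SE × √(1 − r²).
- A gap of one SE (0.20 SD) in the direction opposite to a true 0.33 SD difference cuts the power of the unadjusted test from 37% to 17% (r = 0.5), 3% (r = 0.8) or below 1% (r = 0.9).
- A gap of 1.96 SE (0.40 SD) with no true difference gives a conditional false-positive rate of 13% (r = 0.5) to 33% (r = 0.9).
- A gap of only one SE does not push that rate above 5% at any r examined.

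**The case against.** The strongest reply is that the plan already shows what is needed. SAP 4.4.2 says the evolution of doses will be observed, 4.4.3 derives changes from D0, 7.4.2 has every secondary variable described by pump group, and 7.3 shows baseline dose by group. A reader might infer that a compensating dose rise would be missed altogether. The documents do not support that: the rise and any baseline imbalance would both be visible in the tables. What is missing is a formal between-pump comparison of change with an interval, and any change variable for total dose.

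A reader might also infer that the planned test is biased. It is not. Randomization covers chance imbalance on average, and the overall error rate is held. The fault is low precision, plus vulnerability if an imbalance happens to occur.

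Nor did the SAP clearly drop a promised dose ANCOVA. The synopsis mentions such models in general, but its list of planned secondary tests does not include dose, and protocol 11.2.4 specifies the tests the SAP uses. The two protocol statements still need reconciling.

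It is tempting to add that the dose tests and the primary verdict concern different patients. The primary test is on PP and the dose tests are on ITTm, but SAP 7.4.1 also runs the primary endpoint on ITTm as a sensitivity analysis, so a glucose result exists on the same set.

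Finally, the secondary objectives are descriptive, and no dose margin or power is set. That stands, and it limits the weight of the point.

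**Conclusion.** The point holds as a matter of precision. The only formal dose comparisons are unadjusted, so a modest difference between pumps could go undetected and a chance baseline gap could distort the result in this trial. At SD 12 IU/day and 48 per arm, ANCOVA would narrow the 95% half-width from about 4.9 to between 4.2 (r = 0.5) and 2.1 IU/day (r = 0.9). The gain is small at the lower correlation and large at the higher one. SD and r are assumptions that blinded data should replace, and 48 per arm is a ceiling.

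The endpoint is secondary and unpowered, and nothing here alters the primary non-inferiority test or its error rate. Some readers may take a dose difference as proof of poorer delivery by one pump. With open-label management and patient-set doses it could equally reflect behaviour, and ANCOVA would not separate the two.

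**What to change.** In SAP 7.4.2 item 7, replace the Student and Mann-Whitney tests at V2 and V3 by an ANCOVA of each variable (total, basal and bolus dose, boluses per day), with pump as factor and its D0 value as covariate. Report Medtrum minus Omnipod with the 95% CI on ITTm, and on PP as a supportive analysis.

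In 4.4.3, add the change from D0 in total daily dose. State that no between-group comparison is made for V3 to V4, because only Omnipod-arm patients enter that period. Record the choice in section 6, and reconcile the protocol synopsis with protocol 11.2.4.

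First confirm that D0 dose was captured. Protocol Table 2 appears to mark pump data only from month 1, and the Visit 1 list (7.3) names insulin type but no dose, while SAP 4.4.3 and 7.3 use D0 doses. The Omnipod controller stores 90 days of data (protocol 3.4.2), so extraction may have been possible.

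The cost is SAP wording and a short adaptation of the MIXED code already written for the primary endpoint. Patients without a D0 dose drop out of the model, and their number should be reported.

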7.5 ANALYSIS OF TOLERANCE DURING THE STUDY

Analyses will be performed overall and by pump group on the **tolerance population**. Prior to any analysis, all DM-related incidents and DM-related tolerance will be coded by the MedDRA regulatory medical dictionary (version 20.0 or later).

The number of patients who had at least one tolerance problem will be described. The following criteria will be described for each period and by pump group:

- Irritation/itching (yes; no)
 - If yes, maximum intensity (low; moderate; intense)
- Redness (yes; no)
 - If yes, maximum intensity (low; moderate; intense)
- Other adverse events (yes; no)
 - All other events related to tolerance will be given in a listing.

A summary table (number and percentage of patients with AEs and number of events) by organ system class (OSG) and preferred term (PT) will be presented for the following categories of events by dissociating incidents and tolerance related to the medical device:

- According to the link (device AND procedure)
- According to the link (device OR procedure)
- Depending on the severity
- Depending on the actions taken (de-boosting)

A listing of individual data will be provided describing all the information collected via the eCRF concerning the AE (including duration, resolution, severity criteria, linkage, severity etc.)

7.6 ANALYSES INTERMEDIATES

A descriptive analysis of baseline HbA1c data for the entire population was performed in a blinded fashion at the end of the inclusion period. This analysis is described in section 5.1 (NSN) of this document.

8 STATISTICAL TABLE TEMPLATES

The tables will be presented in the form :

Table xx: Description of quantitative variables	
---	--

		Group A N=xxx	Group B N=xxx	Total N=xxx	p-value
Variable 1	Ν	Х	Х	Х	
	Missing	Х	Х	Х	
	$Mean \pm SD$	$xx.xx \pm xx.xx$	$xx.xx \pm xx.xx$	$xx.xx \pm xx.xx$	
	Median	XX.XX	XX.XX	XX.XX	
	Q1; Q3	xx.xx ; xx.xx	xx.xx ; xx.xx	xx.xx ; xx.xx	
	Min; Max.	xx.xx ; xx.xx	xx.xx ; xx.xx	xx.xx ; xx.xx	

		Group A	Group B	Total	
		N=xxx	N=xxx	N=xxx	p-value
Variable 2	Ν	Х	Х	Х	
	Missing	Х	Х	Х	
	Mean \pm SD	$xx.xx \pm xx.xx$	$xx.xx \pm xx.xx$	$xx.xx \pm xx.xx$	
	Median	XX.XX	XX.XX	XX.XX	
	Q1; Q3	xx.xx ; xx.xx	xx.xx ; xx.xx	xx.xx ; xx.xx	
	Min; Max.	xx.xx ; xx.xx	xx.xx ; xx.xx	xx.xx ; xx.xx	

The 95% Confidence Intervals can be presented in the tables. *Table xx: Description of categorical variables*

		Group A	Group B	Total	
		N=xxx	N=xxx	N=xxx	p-value
Variable 3	Ν	Х	Х	Х	Х
	Missing	Х	Х	Х	Х
	Modality 1	xx (xx.x%)	xx (xx.x%)	xx (xx.x%)	xx (xx.x%)
	Modality 2	xx (xx.x%)	xx (xx.x%)	xx (xx.x%)	xx (xx.x%)
Variable 4	Ν	Х	Х	Х	Х
	Missing	Х	Х	Х	Х
	Modality 1	xx (xx.x%)	xx (xx.x%)	xx (xx.x%)	xx (xx.x%)
	Modality 2	xx (xx.x%)	xx (xx.x%)	xx (xx.x%)	xx (xx.x%)
	Modality 3	xx (xx.x%)	xx (xx.x%)	xx (xx.x%)	xx (xx.x%)

The 95% Confidence Intervals can be presented in the tables. *Table xx: Description of IS by SOC and PT*

	Total (N=xxx)		
SOC and PT			
	EI	n	%
	(1)	(2)	(3)
TOTAL	XX	XX	XX.X
SOC 1	XX	XX	XX.X
SOC 1 - PT 1	XX	XX	XX.X
SOC 1 - PT 2	XX	XX	XX.X
	XX	XX	XX.X
SOC 2	XX	XX	XX.X
SOC 2 - PT 1	XX	XX	XX.X
SOC 2 - PT 2	XX	XX	XX.X
	XX	XX	XX.X

(1) Number of EIs

(2) Number of patients with at least one AE

(3) % of patients with at least one AE

9 **BIBLIOGRAPHY**

1. CNEDiMTS opinion of May 30, 2017. External, portable, programmable insulin pumps.

28. LOB OPEN DATA- 2019

10 LEVEL OF VALIDATION OF ANALYSES

This chapter documents the validation of statistical analysis programs. The level of validation is defined with reference to the "Statistical Analysis Programming" procedure. 3 validation levels are defined:

- *Basic* = At each program execution, the programmer will make sure that his programming is valid. First, the code should be checked to make sure that it matches the expected analyses. Secondly, no error messages should appear in the "log/Journal" window. If this is not the case, the error should be corrected. Warnings and notes such as uninitialized variables, automatic replacement of missing data, data outside the graph area, ... should also be checked. Third, the output of the results should be checked to make sure that the submitted program is what it is supposed to do and that there are no errors in the presentation of the results.
- *NC (non-critical)* = The tables, listings and figures compiled in a single document will be verified by a qualified person other than the program developer with the study's observation book and statistical analysis plan as a support. Spot checks (number of participants, average, minimum, maximum, frequency, number of missing data) will be performed. Comparisons with other data (e.g. comparison of a figure with the source table) will be made.
- *CR (critical)* = A double programming and a comparison of the results will have to be carried out by a qualified person other than the developer of the program. In the event that the checks show discrepancies, the cause will be investigated and the programming will have to be redone if it turns out that the error came from the first programming.

Analyses with a "Basic + CR" level of programming validation	Reference of the Statistical Analysis Plan	
- Populations	Section 7.1.3 " Populations of analysis "	
- Main objective	Section 7.4.1 " Primary endpoint analysis "	

The other analyses and programs have a default validation level of "Basic + NC".
